#### Funder

Imperial NIHR BRC: Imperial Health Care Charity and RM Partners

This protocol describes the CaPaBLE study and provides information about procedures for entering participants. Every care was taken in its drafting, but corrections or amendments may be necessary. These will be circulated to investigators in the study. Problems relating to this study should be referred, in the first instance, to the Chief Investigator.

This study will adhere to the principles outlined in the UK Policy Frame Work for Health and Social Care Research It will be conducted in compliance with the protocol, the Data Protection Act and other regulatory requirements as appropriate.

NHS Imperial College Healthcare

#### **GLOSSARY OF ABBREVIATIONS**

AE	Adverse Event
CaGI	Caregiver Generated Index
CarGoQoL	CareGiver Oncology Quality of Life
CRF	Case Report Form
EORTC	European Organisation for Research and Treatment of Cancer
GBM	Glioblastoma
HGG	High Grade Glioma
HRQoL	Health-related Quality of Life
QoL	Quality of Life
MDT	Multi-Disciplinary Team
MoCA	Montreal Cognitive Assessment
PGI	Patient Generated Index
PIS	Patient Information Sheet
PPI	Patient and Public Involvement
PS	Performance Status
SAE	Serious Adverse Event

#### **KEYWORDS**

Health-related quality of life; brain tumours; caregiver; patient generated index; high grade glioma

#### **STUDY SUMMARY**

TITLE	Caregiver and Patient less-Burden Life Evaluation -Phase II Observational study (CaPaBLE Study)					
DESIGN	Phase II non-randomised pragmatic cohort study of patients and caregivers					
AIMS	Explore the feasibility and acceptability of novel, personalised measures of how an illness and i treatment can affect the areas of life most important to an individual with a brain tumour and their caregivers.					
	Identify the similarities and differences in ratings of health-related quality of life between novel, personalised and standard measures in patients with brain tumours and their caregivers, over a period of 6 months					
	Measure the statistical properties (correlation, variation and stability) of novel, personalised and standard measures over time					
OUTCOME MEASURES	Feasibility and acceptability of novel, personalised measures of HRQoL in patients with brain tumours and their caregivers which will be measured as completion rates)					
	Identify the similarities and differences in ratings of HRQoL between novel, personalised and standard measures in patients with brain tumours and their caregivers, over a period of 6 months					
	Measure correlation, variation and stability between PGI/ CaGI and standard measures over time					
POPULATION	Newly diagnosed/ recurrent high-grade primary brain tumour patients and their caregivers					
ELIGIBILITY	
 
Inclusion Criteria -Patient         
 
Newly diagnosed, or recurrent, high-grade primary brain tumour. We define a high-grade tumour as any grade 3 or 4 primary brain tumour (including meningioma).
 
Newly diagnosed patients intending to undergo neurosurgical biopsy or resection, or to start a course of radical (>=45Gy) radiotherapy or a course of chemoradiotherapy or stereotactic radiotherapy.
 
Recurrent brain tumours patients undergoing further treatment including surgery, chemotherapy or re-irradiation.
 
Performance status 0, 1, or 2
 
Able to provide written informed consent.
 
Intention to attend at least 5 clinic visits over a six-month period to the study site
 
Age 18 years and above
 
Willing to undertake study-specific measures
 
 
 
					

IRAS number 266261

	Inclusion Criteria -Caregiver				
	1.	Main caregiver of patient with newly diagnosed or recurrent high-grade primary			
	brain tumour. 2. Caregiver of patient receiving treatment (surgery and/or radiotherapy/				
	chemotherapy) expected to last >= 3 weeks in total				
	3.	Aged 18 and above			
	4.	Intention to attend at least 5 clinic visits over a six-month period to the study site.			
	5.	Willing to undertake study-specific measures			
	6.	Able to provide written informed consent			
DURATION	Study will be c	ppen for 2 years; Participants will be on study for 6 months			

## Imperial College

## London

#### INTRODUCTION 1.

#### 1.1 BACKGROUND

Despite some advances in treatment, the prognosis for patients with high grade brain tumours remains poor, and it is well recognised that both the disease and its treatment have the potential to affect the day to day lives of patients and their caregivers. However, the only tools currently available to get a formal understanding of quality of life are long questionnaires which do not allow for individuals to express their own opinions about what is important to their lifestyle. Moreover, "quality of life" is a difficult concept to define as its meaning may be different to different people. In addition, the nature of a patient's symptoms due to brain tumours, notably their degree of cognitive impairment, can be a barrier for questionnaire completion. For these reasons, the completion of HRQoL questionnaires, even within the context of a clinical trial, remains poor ((Taphoorn et al., 2010; Wick et al., 2016; Bitterlich and Vordermark, 2017).

Of note when discussing Quality of Life assessment is need to clarify the various terms used within the accompanying literature. Resulting from the diversity of intended uses, there are a variety of terms and associated assessment tools. Terms like "health status" are associated with a persons' disease state and physical performance, these are often clinician reported outcomes and include scales such as the ECOG Performance Scale and Adult Comorbidity Evaluation 27. "Quality of life" is seen as the most subjective term which is associated with an individuals' overall well-being and their view in comparison to expectations (own and societal); QoL questionnaires will include items on standard of living, social integration and personal relationships. "Health Related Quality of Life" is understood to be the impact on QoL in response to health state, this term can incorporate many domains and related questionnaires would include items covering self-care, pain and depression these patient reported outcome tools most commonly used during clinical trials.

Currently the standard HRQoL questionnaire for brain tumour patients used in clinical trials is the EORTC QoL-Core30 (QLQ-C30) with an additional brain tumour module (BN20). In total these questionnaires come to 50 questions, though it is recognised that with the specific nature of brain tumour symptom presentation not all domains may be required for every patient. (Osoba et al., 1996). Methods for item reduction have been trialled through the use of Computerised Adaptive Testing (CAT) however this is a complex process necessitating software implementation (Dirven et al., 2017). Furthermore, the development and validation process for HRQoL questionnaires inherently makes them slow to respond to changes in available clinical treatments. As discussed in the work of the RANO PRO initiative (Dirven et al., 2018), changes to side effect profiles mean that questionnaires developed 10 or more years ago no longer encompass issues of relevance to patients on current treatments.

For caregivers, a diagnosis of a brain tumour can result in negative outcomes for their own quality of life by impacting on areas like finances, free time and their own health needs. These have led to caregiver QoL assessment being included in research priorities set by national think tanks including the James Lind Alliance, as well as being highlighted within our own patient and public involvement feedback sessions. One of the most recent caregiver specific QoL tool is the CareGiver Oncology

CaPaBLE Protocol V3.3 14/04/2020

IRAS number 266261

## Imperial College Healthcare

Quality of Life (CarGOQoL) questionnaire. This is a validated tool for use with partners, parents and children. Its 29 items cover 10 domains (psychological well-being, burden, relationship with healthcare, administration and finances, coping, physical well-being, self-esteem, leisure time, social support and private life) (M. *et al.*, 2007, 2018; Brown *et al.*, 2008; Munoz *et al.*, 2008; Whalen and Buchholz, 2009; Flores *et al.*, 2014; Piil *et al.*, 2015; Baumstarck *et al.*, 2018; Reblin *et al.*, 2018).

One approach to reducing questionnaire burden is to use a process known as patient generated index (PGI) (Ruta *et al.*, 1994). In contrast to traditional QoL questionnaires which have defined domains to complete, the PGI allows individuals to suggest areas of their own lifestyle they consider to be important and provides a method for rating their significance. The process of using PGI has been successfully used with cancer patients, these studies have also highlighted the brain tumour patient group as potentially benefitting from the application of this tool in light of the specific symptoms each patient may present with. Methods similar to the PGI have been used with caregivers, though most commonly in the paediatric and dementia care settings where the opinions raised are as a proxy measure for patient QoL (Hogan *et al.*, 2013; Tang *et al.*, 2014; Aburub *et al.*, 2016a; H. *et al.*, 2016).

#### 1.2 RATIONALE FOR CURRENT STUDY

Outside of clinical trials, the use of repeat QoL measurement for brain tumour patients and their caregivers in regular oncology follow up is poor. This is largely due to the same factors which limit completion rates of standard QoL questionnaires during trials, notably the lengthy questionnaire formats and complication of neurological deficit following disease and treatment.

Currently, QoL concerns are routinely recorded using the Holistic Needs Assessment. However, the outcome of this tool does not include a numerical QoL outcome and cannot easily track changes over time. In routine practice, this is also not used with caregivers.

To try to facilitate higher QoL completion rates with more personalised outputs, the CaPaBLE study intends to assess the feasibility of using the PGI process with patients diagnosed with brain tumours. Additionally, we will use the same tool to assess QoL of their main caregiver - a novel method we are terming the Caregiver Generated Index (CaGI). The results of PGI and CaGI will be compared to existing standard QoL questionnaires to get an understanding how well they capture the impact of living with this new diagnosis.

Our intention is that, if proved feasible, the use of PGI and CaGI in routine practice would deliver longitudinal patient QoL data which would help identify areas of need and direct the use of suitable services.

#### 2. STUDY OBJECTIVES

#### 2.1 AIMS

- 1. Explore the feasibility and acceptability of novel, personalised measures of HRQoL in patients with brain tumours and their caregivers.
- 2. Identify the similarities and differences in ratings of health-related quality of life between personalised and standard measures in patients with brain tumours and their caregivers, over a period of 6 months
- 3. Measure correlation, variation and stability of novel personalised measures and standard measures over time

#### 2.2 OBJECTIVES

- 1. To explore the feasibility and acceptability of using PGI/ CaGI to assess HRQoL over time in patients with high-grade glioma (HGG) and their caregivers
- 2. To assess how changes in HRQoL as measured through standard approaches and personalised subsets + PGI/ CaGI relate to one another
- 3. To assess the impact of high grade, malignant primary brain tumours on quality of life in newly diagnosed patients and track changes in reported QoL throughout treatment and disease progression
- 4. To assess the impact on quality of life of being a caregiver for a patient with newly diagnosed, high grade, malignant primary brain tumours and track changes in reported caregiver QoL throughout treatment and disease progression
- 5. To identify differences and relationships between QoL scores expressed by patients and caregivers over time
- 6. To assess patient, caregiver and professional views on the comparative benefits and drawbacks of standard approaches and PGI/ CaGI

#### 3. STUDY DESIGN

CaPaBLE is a prospective, observational, phase 2 non-randomised pragmatic cohort study of patients and caregivers, from diagnosis to six months.

All baseline assessments will be carried out at the local site as these will normally be done at the time of consent. Once consent has been taken in person, the option of video or telephone consultations will be considered on a patient/ caregiver basis by the treating clinical team. This is an already established service provided by the Neuro-oncology team at Imperial NHS Trust for those that are unable to attend the appointment in person.

# Imperial College Healthcare

#### 3.1 SAMPLE SIZE

The target sample size for this observation, longitudinal study is 130 (80 patients and 50 caregivers), using a 20% patient and caregiver dropout rate. Our study design is based on a close reading of previous studies. Based on previous work, we estimated that a sample size of 80 patients is needed to allow for an analytical sample of 60. We expect that not all caregivers will participate, and thus we allow for a differential recruitment.

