#### 8.1 STUDY DESIGN AND SAMPLE SIZE

Our study design is based on a close reading of previous studies, and our target sample size is 130 patients and caregivers. Based on previous work, we estimated that a sample size of 80 patients is needed to allow for an analytical sample of 60 (Hogan *et al.*, 2013; Tang *et al.*, 2014; Aburub *et al.*, 2016b). We expect that not all caregivers will participate, and thus we allow for a differential recruitment of 50 caregivers. Previous work exploring the use of PGI has typically enrolled 30 - 80 patients. Our work should place us towards the top end of this range.

Formal statistical planning is difficult without knowing rates of completion and drop-out. However, if we want to estimate the concordance (as agreement between standard QoL measures and PGI) using Spearman's rank correlation coefficient, then there is a formula to calculate these confidence intervals. If we assume that the true correlation coefficient is ~0.5 (in line with previous work in 55 patients with traumatic brain injury and 192 patients with a range of cancers) then if we find an r =

0.5 and analytical n = 60 the 95% confidence intervals for the r value are 0.28 - 0.67. In the caregiver cohort, if calculated r = 0.5 and n = 30 then the 95% confidence intervals on r is 0.17 - 0.73.

We accept that these 95% confidence intervals are large (although in line with the literature) which is why this is a feasibility and pilot study.

The main aim of CaPaBLE is to demonstrate feasibility and acceptability of using the PGI and CaGI in patients with brain tumours and caregivers. We will assess face and content validity of the PGI by assessing areas of patients' lives affected by the cancer and the treatment and comparing those to domains in the standard measures.

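### The stated 20% dropout does not give the analysable numbers of 60 and 30, and the intervals labelled Spearman are Pearson intervals that are slightly too narrow (minor)

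*Protocol*

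**What the plan says.** Section 3.1 of the protocol gives the recruitment target: "The target sample size for this observation, longitudinal study is 130 (80 patients and 50 caregivers"), and adds "using a 20% patient and caregiver dropout rate". It then says of the patients that "we estimated that a sample size of 80 patients is needed to allow for an analytical sample of 60".

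Section 8.1 repeats the step from 80 to 60. For the second group it says "thus we allow for a differential recruitment of 50 caregivers", the only caregiver recruitment figure. It remarks that formal planning is hard while completion and drop-out rates are unknown, and then gives a precision calculation: "using Spearman's rank correlation coefficient, then there is a formula to calculate these confidence intervals". The formula is not named. The planning value is given as "If we assume that the true correlation coefficient is ~0.5". The results are "0.5 and analytical n = 60 the 95% confidence intervals for the r value are 0.28 - 0.67" for patients and "if calculated r = 0.5 and n = 30 then the 95% confidence intervals on r is 0.17 - 0.73" for caregivers. The section accepts that these intervals are wide and describes the study as feasibility and pilot work. It also supports the size by the range of 30 to 80 patients in earlier studies of the PGI.

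**The concern.** There are two separate mismatches.

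First, one dropout rate is stated for both groups, but the analysable numbers used for precision do not follow from it in either group. The discrepancy is modest for patients and large for caregivers. Feasibility is the main aim (section 8.1) and is to be judged by completion rates (section 3.8), so expected attrition is a central planning figure. As written, a reader cannot tell whether ending with 30 of 50 caregivers would be as planned or twice the planned loss.

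Second, section 8.1 names Spearman's coefficient, but the printed intervals have the width that belongs to Pearson's. The sampling variance of Fisher's z is larger for Spearman's coefficient, so the precision is stated slightly too favourably.

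**Working it through.** **Inputs.** From section 3.1: 80 patients, 50 caregivers, 20% dropout in both, 60 analysable patients. From section 8.1: r = 0.5; n = 60 and n = 30; two-sided 95% intervals of 0.28 to 0.67 and 0.17 to 0.73.

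**Dropout.**
- Forward: 80 × 0.8 = 64, not 60; 50 × 0.8 = 40, not 30.
- Implied loss: 1 − 60/80 = 25%; 1 − 30/50 = 40%.
- Backward: 60/0.8 = 75, not 80; 30/0.8 = 37.5, so 38, not 50.
- The common shortcut N × 1.2 gives 72 and 36, which does not match either.
- If 20% is dropout alone and the rest is incomplete data, the completion needed among those retained is 60/64 = 94% for patients and 30/40 = 75% for caregivers. Neither figure is stated.

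**Reproducing the printed intervals.** The Pearson form is tanh(atanh(r) ± 1.96/√(n − 3)), with atanh(0.5) = 0.5493.
- n = 60: 0.5493 ± 1.96/√57 gives 0.282 to 0.669.
- n = 30: 0.5493 ± 1.96/√27 gives 0.170 to 0.729.

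Both agree with section 8.1 to two decimals, so the printed figures are the Pearson Fisher-z intervals.

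**Spearman intervals.** The form is the same, with a variance for Spearman's z in place of 1/(n − 3). The protocol names no variance, so three standard choices are shown:
- A: (1 + r²/2)/(n − 3) (Bonett-Wright), which is 1.125/(n − 3) at r = 0.5
- B: 1.06/(n − 3) (Fieller)
- C: 1/(n − 2) + |z|/(6n + 4√n) (Caruso-Cliff)

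| n | Pearson form | A | B | C |
|---|---|---|---|---|
| 60 | 0.282–0.669 | 0.267–0.678 | 0.275–0.673 | 0.275–0.673 |
| 30 | 0.170–0.729 | 0.148–0.740 | 0.160–0.734 | 0.164–0.732 |
| 64 | 0.290–0.664 | 0.276–0.673 | 0.283–0.668 | 0.283–0.669 |
| 40 | 0.223–0.702 | 0.205–0.712 | 0.214–0.707 | 0.216–0.706 |

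All three Spearman forms are wider than the printed intervals at n = 60 and n = 30. The limits move by about 0.004 to 0.015 at n = 60 and 0.003 to 0.022 at n = 30.

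**Coverage.** Simulation used bivariate normal data with a true Spearman value of 0.5, 40,000 samples per n, and a Monte Carlo standard error of about √(0.95 × 0.05/40,000) = 0.1 percentage points.

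| n | Pearson form | A | B |
|---|---|---|---|
| 60 | 94.0% | 95.4% | 94.7% |
| 30 | 94.3% | 95.7% | 95.0% |

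The simulated variance of z times (n − 3) was 1.07 at n = 60 and 1.06 at n = 30, against 1 under the Pearson form.

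**The case against.** **Dropout need not be the only loss.** Section 8.1 treats completion and drop-out as two rates, and sections 1.1 and 1.2 say that questionnaire completion is poor in this population. An analysable number below the retained number is therefore to be expected. For patients the step from 64 to 60 is small. This is a fair explanation of how the figures may have arisen, but the protocol does not give it, and for caregivers it would need a quarter of those retained to be unanalysable. The expectation that some caregivers will not take part explains recruiting 50 rather than 80, not a fall from 50 to 30.

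**A reader might infer that the plan assumes 40% caregiver dropout.** The text does not go that far. It never derives 30 from 50, and it offers the caregiver interval conditionally. What can be said is that 50 is the only caregiver recruitment figure, 30 the only caregiver n in the precision statement, and the step between them is unexplained.

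**A reader might infer that the study is too small.** The reverse holds. At the stated 20% dropout, more participants would be analysable (64 and 40) than the precision statement uses.

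**A reader might infer that the intervals are miscalculated or materially misleading.** They follow exactly from r = 0.5 with n = 60 and n = 30 under the Pearson formula. Under variance B they would read 0.27 to 0.67 and 0.16 to 0.73, a change of 0.01 in each lower limit. With n = 64 and either A or B, the patient interval is 0.28 to 0.67, as printed. The choice among Spearman variances is partly preference: A over-covers slightly in the simulation. The method for reported intervals may also be set in a statistical analysis plan that is not at hand, so under-coverage of the final results cannot be asserted.

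**Little depends on these figures.** The size also rests on earlier PGI studies, the protocol concedes that the intervals are wide, and no test, threshold or decision is tied to them. This stands, and it sets the grade.

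**Conclusion.** Minor, but wrong as written on both counts.

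The dropout mismatch is the more substantive part: 20% stated against a total loss of 25% of patients and 40% of caregivers. It rests only on figures printed in the protocol, plus the reading that 30 is the analysable part of the 50 caregivers. It is conservative and calls for no extra recruitment.

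The Pearson intervals given for Spearman's coefficient are too narrow by at most about 0.02 at any limit, with coverage of about 94% instead of 95%. The exact size depends on the Spearman variance chosen and, for coverage, on bivariate normal data with a true value of 0.5. The direction is the same under all three variances tried. The conclusion that precision is low is unchanged.

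**What to change.** **Sections 3.1 and 8.1, attrition.** Use one consistent set of figures. Either:
- keep n = 60 and 30 and state the total planned loss (dropout plus incomplete questionnaires) as 25% of patients and 40% of caregivers, with the reason for the difference; or
- keep 20% and base precision on n = 64 and 40.

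**Section 8.1, intervals.** Name a Spearman variance and recompute.
- With (1 + r²/2)/(n − 3): 0.27 to 0.68 at n = 60 and 0.15 to 0.74 at n = 30, or 0.28 to 0.67 at n = 64 and 0.20 to 0.71 at n = 40.
- With 1.06/(n − 3): 0.27 to 0.67 at n = 60 and 0.16 to 0.73 at n = 30, or 0.28 to 0.67 at n = 64 and 0.21 to 0.71 at n = 40.

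Use the same named method, or a bootstrap, for the Spearman intervals that are reported.

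**Cost.** Rewording in two sections, with no extra participants. The stated precision becomes slightly less favourable if n = 60 and 30 are kept. With n = 64 and 40 the patient interval stays as printed, and the caregiver interval narrows from a width of 0.73 − 0.17 = 0.56 to 0.71 − 0.20 = 0.51 under the first variance.

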#### 3.2 PARTICIPANTS

The target population of this study is patients with newly diagnosed (pre first treatment) or recurrent high-grade primary brain tumour and their caregivers. To best reflect clinical practice, we define a high-grade tumour as any grade 3 or 4 primary brain tumour (including meningioma). We will enrol participants from the joint Neuro-Oncology clinic, as early as possible in their diagnostic pathway. We will enrol those with brain tumours who have recently been diagnosed and are about to start a course of treatment or those diagnosed with recurrent disease and undergoing a second line treatment.

People who take on the caregiver role do not identify always themselves as caregiver therefore, for the purpose of this study we will use Macmillan's definition of a caregiver - 'Someone who, unpaid, looks after a person with cancer who couldn't manage without this help'. In practice we would also include any person identified by the patient as being essential for assisting in the management of their day-to-day and clinical needs.

